5.2 Background

The target population of lenalidomide in MDS with del(5q) has for a long time been erroneously identified with the so-called "del(5q) syndrome," first described by Van den Berghe in 1974 (Van den Berghe, 1974), and characterized by refractory macrocytic anemia, normal or elevated platelet counts associated with erythroid hypoplasia, dyserythropoiesis, modest excess of myeloblasts, hypolobulated megakaryocytes, and del(5q) in the presence of an otherwise normal karyotype. This syndrome is prevalent in females and has a low propensity to evolve into AML. In a case-series from the Düsseldorf MDS Registry, the cumulative incidence of AML among patients with the del(5q) syndrome was reported to be 8% (Germing, 2000). In contrast to patients with the "del(5q) syndrome," patients with IPSS low-/int-1–risk MDS with del(5q) also have well-defined additional risk factors such as additional cytogenetic abnormalities (Schanz, 2012), excess blasts (5% to 10%), severe anemia, and transfusion dependency (Malcovati, 2006; Malcovati, 2011). Depending on the presence of additional risk factors, the survival of these patients can be as low as 7 months.

Patients with del(5q) and complex karyotype have a very high risk of leukemic progression when compared to patients with isolated del(5q) or del(5q) + 1 additional cytogenetic abnormality. In a series of 541 patients with MDS and del(5q), patients with isolated del(5q) had a time to 25% probability of AML transformation of 65 months compared to the same rate of AML transformation of 14.9 months for patients with del(5q) + 1 additional cytogenetic abnormality and of only 4.7 months for patients with a complex karyotype (Mallo, 2011).

Data from the most complete series of untreated IPSS low- or int-1–risk MDS patients with del(5q) with survival data available was published by the Düsseldorf MDS group, who describe the natural history of the disease in a cohort of 381 patients included in the disease registry and treated only with supportive care (Germing, 2012). Patients with transfusion dependence had a 2-year cumulative risk of AML of 4.9% and a 5-year AML risk of 17.6%, higher than the figure previously reported by the same group for the "del(5q) syndrome."

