7.7.2 Descriptive Analyses of Lenalidomide Use Patterns in Routine Clinical Practice

The number and percent of MDS patients (both prevalent and incident) who have received at least one dose of lenalidomide will be characterized as in the labeled indication (ie, transfusion-dependent IPSS low- or int-1-risk MDS with an isolated del(5q) cytogenetic abnormality) or outside of the EU labeled indication (ie, patients with any type of MDS other than transfusion-dependent IPSS low- or int-1-risk MDS with isolated del(5q)). The rate of patients treated for MDS outside of the EU approved indication (off-label), will be provided with its 95% CI. MDS patients who are outside of the labeled EU indication will be further characterized as to the following:

- IPSS Status (Int-2 or High).
- Presence of additional cytogenetic abnormalities (yes/no) and characterization of type of additional cytogenetic abnormalities based upon the Revised International Prognostic Scoring System (IPSS-R) classification.
- Lack of documentation of transfusion-dependent status or documentation of transfusion burden insufficient to meet accepted criteria for transfusion-dependence.

It is acknowledged that patients who are out of the labeled indication may satisfy more than one of the disqualifying criteria. For the purpose of the current retrospective MDS PASS, transfusion-dependence is defined as requiring ≥ 2 RBC units over an 8-week period prior to the date of the first dose of lenalidomide treatment (due to MDS-related causes and not because of hemorrhage, trauma, or other acute cause).

In addition, patients within and outside the EU labeled indication will be characterized as to other demographic and clinical characteristics (ie, age, gender, duration of MDS, CBCs [WBC, platelets, hemoglobin levels], ferritin level, time from diagnosis to treatment, and RBC transfusion burden), relevant medical history, co-morbidities, previous MDS treatments, and current co-medications.

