7.7.3 Safety Analyses

Safety analyses will be based on both the on- and off-label cohorts.

The cumulative incidence of progression to AML will be calculated and stratified according to predictive factors; 95% CIs will be calculated for each of the two cohorts. Aggregated data will be listed by country when possible.

Each registry will be requested to produce Kaplan-Meier curves for on- and off-label patients separately and to calculate the hazard ratio of on- versus off-label patients. They will also be requested to perform multivariate analyses using a Cox model including and on-/off-label indication and prognostic factors as described in the Statistical Analysis Plan on their own individual data. The respective outcomes will be provided by each registry to the study sponsor. Safety for the on- and off-label cohorts will be determined based on the incidence of reported hematological and non-hematological adverse events including SPM other than AML (which is considered as disease progression in patients with MDS). In particular episodes of neutropenia, thrombocytopenia, venous thromboembolic events, infections, bleeding, major cardiac events and SPM will be collected throughout the observational period of a patient in both cohorts as part of the clinical routine.

Due to the secondary use of the data, individual data may not be available. In these conditions, no explorative analyses on confounding or risk factors is foreseen in the protocol, except for progression to AML.

As there is no international standard to define transfusion dependence and there is a risk of error in transfusion coding, an additional sensitivity analysis will be completed to assess the impact of transfusion on the size of the on- and off-label cohorts. This sensitivity analysis will describe the proportion of off-label patients based only on IPSS categories other than low and int-1, and any karyotype other than isolated del(5q).

All safety analyses will be mainly descriptive or explorative in nature.

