7.7.4 Interim Descriptive Report

An interim descriptive report was prepared 1 year after study start. Within the interim descriptive report, available data on eligible patients regarding the pattern of use of lenalidomide within and outside the EU approved indication, namely the distribution of MDS patients according to predefined categories (eg, transfusion-dependent IPSS low- or int-1-risk MDS with isolated del(5q), or with additional cytogenetic abnormalities, or IPSS risk categories int-2 or high, or patients with MDS without del(5q)) was presented. On 29-Mar-2019, the first interim descriptive report was submitted to the Pharmacovigilance Risk Assessment Committee (PRAC) in order to discuss if the data collected on lenalidomide use, across different groups of MDS patients, are sufficient to allow successful completion of this study. The Assessment Report adopted by the CHMP on 27-Jun-2019 included a request to submit another interim descriptive report in Quarter (Q)1 2020. On 27-Mar-2020, the second interim descriptive report was submitted to PRAC (EMEA/H/C/000717/ANX/041.8). The final Assessment Report, adopted by the CHMP on 10-Dec-2020, concluded that the post-authorisation measure for the second interim report was fulfilled with no further action required.

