7.9 Limitations of the Research Methods

A drug-utilisation study of lenalidomide in the commercial setting is an important addition to the pharmacovigilance activities for evaluating the safety and use of lenalidomide. This proposed retrospective drug-utilisation study will help determine the extent of use of lenalidomide in MDS by cohort (on-label, off-label, and overall). This will provide valuable information by which to determine the number and type of patients who are being treated outside of the EU approved indication and the consequences of such lenalidomide prescribing vis-à-vis the safety profile of the drug.

To provide a representative analysis of the European population, the study will include information from at least 10 EU countries that have lenalidomide reimbursement for the MDS indication, including data from the EUMDS Registry (de Swart, 2015). More EU countries will potentially be included, once they gain reimbursement for the MDS indication. As data collection for this study is retrospective and relies on existing data sources, there is a significant risk that there will be

missing information. To address this, a common set of variables and other data elements will be defined and will be the same across all sources. This will also facilitate the pooling of aggregated data for analysis. Pooling of raw data is not feasible because raw data will be held by the data owners (ie, data sources in Section 7.4).

Since this study is retrospective and based on secondary data that were collected in several registries, these registries may differ by their initial purpose, the characteristics of their patient populations and availability of some information. The sponsor will define and standardize the criteria for data use both in the aggregated datasets and in the pseudonymized datasets; however, it is expected that a level of inter-registry heterogeneity will exist, which may be a consideration for the meta-analyses. Consequently, the interpretation of results will be made with caution and consider important differences across the original data sources.

Assessing the safety of lenalidomide in a retrospective study will encounter the same lost-to-follow-up issues common to all follow-up studies. A comparison of baseline and treatment characteristics between patients who are and are not lost to follow-up as they were followed in the registry (or other data sources) will enable this form of selection bias to be evaluated where applicable.

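### Section 7.7.3 pools the off-label cohort for the Kaplan-Meier curves, the crude on/off hazard ratio and all AE and SPM incidences, although the reasons for being off-label carry opposite expected AML risks

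*Protocol*

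**What the plan says.** Section 7.2.1 defines the off-label cohort by exclusion: any MDS that is not transfusion-dependent, IPSS low/int-1 and isolated del(5q) at once.

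For drug use, Section 7.7.2 opens this group up: "MDS patients who are outside of the labeled EU indication will be further characterized as to the following". It lists IPSS int-2 or high, additional cytogenetic abnormalities, and transfusion dependence that is either not met or not documented. It accepts that a patient may meet more than one criterion. Section 7.7.4, on the interim report, speaks of "the distribution of MDS patients according to predefined categories", and its examples add MDS without del(5q).

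For safety, Section 7.7.3 plans:
- AML incidence: "The cumulative incidence of progression to AML will be calculated and stratified according to predictive factors; 95% CIs will be calculated for each of the" (the sentence ends by naming the on- and off-label groups together).
- From each registry, one curve per cohort and one hazard ratio: "produce Kaplan-Meier curves for on- and off-label patients separately and to calculate the hazard ratio of on- versus off-label patients".
- From each registry, "multivariate analyses using a Cox model including and on-/off-label indication and prognostic factors as described in the Statistical Analysis Plan".
- AE and SPM incidence for the on- and off-label cohorts, with the limit that "no explorative analyses on confounding or risk factors is foreseen in the protocol, except for progression to AML".

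Section 7.9 gives the purpose: to "determine the number and type of patients who are being treated outside of the EU approved indication and the consequences of such lenalidomide prescribing".

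**The concern.** The routes into the off-label cohort do not point the same way on AML. Section 5.2 reports that "patients with isolated del(5q) had a time to 25% probability of AML transformation of 65 months", against 14.9 months with one additional abnormality and 4.7 months with a complex karyotype. The same section calls higher transfusion dependence a known risk factor for AML. A patient with isolated del(5q), low IPSS risk and no transfusion dependence is thus off-label at lower expected risk than the on-label cohort. A patient with a complex karyotype is off-label at much higher expected risk.

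One off-label curve, one crude hazard ratio and one off-label incidence per AE average over these patients. The result moves with the proportions in the registries even if lenalidomide does the same thing in every patient. Section 7.9 promises to link the type of off-label patient to the consequences of prescribing. The categories that would make that link are in Section 7.7.2, but 7.7.3 does not carry them into the safety results.

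**Working it through.** **1. The plan's own figures.** Section 7.5 gives 17% AML in 230 off-label patients with a 95% CI of 12.3% to 22.4%. The exact (Clopper-Pearson) interval for 39/230 is 12.3% to 22.4%. For 50% of 460, the Wald interval is 0.50 ± 1.96 × √(0.25/460) = 45.4% to 54.6%. Both reproduce. The 17% is planned for the pooled off-label cohort.

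**2. The contrast in Section 5.2.** Assume constant hazards and no competing deaths. Hazard = −ln(0.75)/T; 24-month risk = 1 − exp(−24 × hazard).

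| Group | T (months) | Hazard per month | Ratio to isolated | 24-month AML |
|---|---|---|---|---|
| Isolated del(5q) | 65 | 0.00443 | 1.0 | 10.1% |
| One additional abnormality | 14.9 | 0.01931 | 4.36 | 37.1% |
| Complex karyotype | 4.7 | 0.06121 | 13.8 | 77.0% |

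**3. Effect of mix alone.** The mixes are assumed.
- 80/10/10: 0.8 × 10.1 + 0.1 × 37.1 + 0.1 × 77.0 = 19.5%.
- 40/30/30: 0.4 × 10.1 + 0.3 × 37.1 + 0.3 × 77.0 = 38.3%.

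The pooled figure roughly doubles with identical patient-level risks.

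**4. Can opposite directions balance?** Rough anchor for the lower-risk group, from Section 5.2: 8% AML in the del(5q) syndrome (no time point given) against 17.6% at 5 years in transfusion-dependent del(5q) patients. The ratio is ln(0.92)/ln(0.824) = 0.43. For the higher-risk group take 4.36 from step 2. With on-label risk 17%, risk at a given hazard ratio (HR) = 1 − 0.83^HR:
- HR 0.43: 7.7%.
- HR 4.36: 55.6%.
- Higher-risk share giving a pooled 17%: (17 − 7.7)/(55.6 − 7.7) = 19%, about 45 of 230.
- With half higher-risk: (7.7 + 55.6)/2 ≈ 32%.

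Over lower HRs of 0.43, 0.5 and 0.7 and higher HRs of 2, 3, 4.36 and 13.8, the balancing share runs from 6% to 40%.

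**5. Crude hazard ratio.** Simulated Cox fits used 40,000 patients per cohort, on-label risk 17.6% at 60 months, and off-label strata at HR 0.43 and 4.36. Figures are off versus on; the protocol asks for the reciprocal.

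| Higher-risk share | Censored at 24 months | Censored at 60 months |
|---|---|---|
| 0% | 0.44 | 0.42 |
| 15% | 0.95 | 0.90 |
| 20% | 1.15 | 0.99 |
| 50% | 2.22 | 2.04 |
| 100% | 4.37 | 4.36 |

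**6. What a breakdown would show.** Suppose 52 higher-risk patients with 29 AML cases and 178 lower-risk patients with 14. Pooled this is 43/230 = 18.7%, close to the planned 17%. By stratum, the exact 95% CIs are 41.3% to 69.5% and 4.4% to 12.8%, which do not overlap.

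**The case against.** A reader might infer that every safety result treats off-label patients as one group. That is not so. AML cumulative incidence is to be stratified by predictive factors, and the Cox model adds prognostic factors. The Study Size part of the Abstract also says the curves and hazard ratios will be adjusted for confounding and risk factors. The factor list is left to the SAP, which is not at hand and may well name IPSS, karyotype and transfusion burden. Leaving the list there is no fault.

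A reader might also infer that the off-label results mainly reflect case mix, or that the hazard ratio will cancel to about 1. The document does not support either, because it gives no split of off-label reasons. Both mixes in step 3 lie above the isolated-del(5q) risk and show no cancellation. Balance needs a particular mix. MDS without del(5q) has no AML figure in the protocol, and patients with undocumented transfusion status have unknown risk.

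Finally, the Abstract disclaims any formal on/off comparison, Section 7.7.3 calls the safety analyses mainly descriptive or explorative, and Section 7.9 promises cautious interpretation. Section 7.7.3 also says why further risk-factor work is limited: patient-level data may be lacking.

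These points narrow the concern but do not remove it. Neither AML safeguard is tied in the protocol to the reason for off-label use. Label status is itself defined by IPSS, karyotype and transfusion dependence, so an on/off term adjusted for those factors has little separate meaning. The model is also fitted registry by registry. For AEs and SPMs the protocol itself rules out further risk-factor analysis, which leaves only the two-cohort split. A descriptive result still needs a group that can be described.

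**Conclusion.** The point holds in this limited form: the Kaplan-Meier curves, the crude hazard ratio and all AE and SPM incidences pool off-label patients whose expected AML risks run in opposite directions, and the planned AML analyses remedy this only in part. The pooled off-label AML figure and crude hazard ratio may largely reflect case mix. In the illustration, the crude off/on hazard ratio runs from about 0.4 to 4.4 with mix alone, and values near 1 arise at about 15% to 20% higher-risk patients. This rests on constant hazards, no competing deaths, approximate anchors from different series, and an off-label mix that the document does not give. It shows what is possible, not what will be found. This is a cheap improvement, not a flaw that invalidates the study.

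**What to change.** In Section 7.7.3, add descriptive tables of AML cumulative incidence, each listed AE category and SPM by the off-label categories of Section 7.7.2 plus MDS without del(5q), where data allow, beside the on-label cohort. Within them:
- Show one additional abnormality separately from complex karyotype, since Section 5.2 puts them far apart.
- Show documented non-dependence separately from undocumented transfusion status, since the second is a data gap and not a risk group.
- Note that the categories overlap, as Section 7.7.2 already accepts.

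Keep the pooled off-label total. State that the on/off hazard ratio is descriptive, depends on case mix and is to be read only beside this breakdown.

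Cost: a few more tables. The classifying variables are already to be collected as available (Tables 3 and 4), and Section 7.4 provides for pseudonymised registry datasets to reach the sponsor. The downside is small groups. Four equal groups from 230 would hold about 57 patients each, and 10 AML cases in 57 (17.5%) has an exact 95% CI of about 8.7% to 29.9%. Real groups will be unequal and some smaller.

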The cumulative incidence of progression to AML will be descriptive and stratified according to risk factors; 95% CIs will be calculated for each of the two cohorts.

Each registry will be requested to produce Kaplan-Meier curves for on- and off-label patients separately and to calculate the hazard ratio of on- versus off-label patients. They will also be requested to perform multivariate analyses using a Cox model including and on-/off-label indication and prognostic factors as described in the Statistical Analysis Plan on their own individual data. The respective outcomes will be provided by each registry to the study sponsor. Safety for both on- and off-label cohorts will be determined based on the incidence and severity (using AE definitions from NCI CTCAE where feasible) of reported hematological and non-hematological adverse events, including SPM other than AML (which considered as disease progression in patients with MDS). In particular episodes of neutropenia, thrombocytopenia, venous thromboembolic events, infections, bleeding, major cardiac events and SPM will be collected throughout the retrospective observational period as part of the clinical routine.

As there is no international standard to define transfusion dependence and there is a risk of error in transfusion coding, an additional sensitivity analysis will be completed to assess the impact of transfusion on the size of the on- and off-label cohorts. This sensitivity analysis will describe the proportion of off-label patients based only on IPSS categories other than low and int-1, and any karyotype other than isolated del(5q).

All safety analyses will be mainly descriptive or explorative in nature.

Interim Descriptive Report:

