An interim descriptive report was prepared 1 year after study start. Within the interim descriptive report, available data on eligible patients regarding the pattern of use of lenalidomide within and outside the EU approved indication, namely the distribution of MDS patients according to predefined categories (eg, transfusion-dependent IPSS low- or int-1-risk MDS with isolated del(5q), or with additional cytogenetic abnormalities, or IPSS risk categories int-2 or high, or patients with MDS without del(5q)) was presented. On 29-Mar-2019, the first interim descriptive report was submitted to the Pharmacovigilance Risk Assessment Committee (PRAC) in order to discuss if the data collected on lenalidomide use, across different groups of MDS patients, are sufficient to allow successful completion of this study. The Assessment Report adopted by the CHMP on 27-Jun-2019 included a request to submit another interim descriptive report in Quarter (Q)1 2020. On 27-Mar-2020, the second interim descriptive report was submitted to PRAC (EMEA/H/C/000717/ANX/041.8). The final Assessment Report, adopted by the CHMP on 10-Dec-2020, concluded that the post-authorisation measure for the second interim report was fulfilled with no further action required.

The final data analysis will occur after at least 460 patients have been included and will be based on data from all eligible patients available at that time.

Data will be collected for both on- and off-label patients, to cover the period from date of first lenalidomide dose (baseline) until the date of death or last follow-up available at the time of the retrospective data collection (whichever occurs first) including for patients lost to follow-up or who discontinue the drug for any reason. Data collected at baseline will include those data that could have been generated earlier but are relevant at the baseline date (for example, information related to diagnosis).

Time to progression to AML or time to any other kind of event will be counted from the date of first lenalidomide dose (baseline).

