CHF = congestive heart failure; EPO = erythropoietin; EU = European Union; IPSS = International Prognostic Scoring System; IPSS-R = revised IPSS; MDS = myelodysplastic syndromes; MI = myocardial infarction; NMSC = non-melanoma skin cancer; PD = progression of disease; VTE = venous thromboembolic event; WHO = World Health Organization,

^a As far as available in data sources and as per clinical practice

^b Cytogenetic risks will be categorized as described in the new cytogenetic scoring system (Schanz, 2012) that has been integrated into the IPSS-R (Greenberg, 2012).

Table 4: Therapy and Other Treatment Variables for Both On- and Off-label Cohorts

Variables ^a	
Lenalidomide Treatment	Indication of use, starting dose, dose adjustments, dose interruptions
Other MDS medications	Current use (yes, no); dose, response, duration of use
Prior ESA Treatment	Prior use (yes, no); prior response (yes/no), most recent treatment, duration of treatment
Other Prior MDS Treatments	Prior use (yes, no); prior response (yes/no), most recent treatment, duration of treatment
Concurrent ESA Use	Current use (yes, no); dose, response, duration of use
Concomitant Medications	Concomitant medications, duration of treatment
RBC transfusion	Yes/no, number of units over last 8 weeks (baseline and until PD)
Con = concomitant ESA	= erythropoiesis-stimulating agent. MDS = myelodysplastic syndromes

Con = concomitant; ESA = erythropoiesis-stimulating agent; MDS = myelodysplastic syndromes; Meds = medications; PD = progression of disease; RBC = red blood cell.

^a As far as available in data sources and as per clinical practice

Variables ^a	
Progression to AML ^b	Yes/no, date of event, and method of documentation
Death	Date and cause of death, and method of documentation
Adverse Events	Date of event (incidence) (using case definitions from NCI CTCAE where feasible) of hematologic and non-hematologic adverse events, including but not limited to neutropenia, thrombocytopenia, VTEs, infections, bleeding, and major cardiac events
SPM (Invasive [hematologic and solid tumors] and NMSC) ^c	Yes/no, date of event, and method of documentation

Table 5: Outcome Variables for Safety for Both On- and Off-label Cohorts

AML = acute myeloid leukemia; CTCAE = Common Terminology Criteria for Adverse Events; NCI = National Cancer Institute; NMSC = non-melanoma skin cancer; SPM = second primary malignancy; VTE = venous thromboembolic event.

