9 MANAGEMENT AND REPORTING OF ADVERSE EVENTS/ADVERSE REACTIONS

Study MDS-012 is a retrospective drug-utilisation study that is based upon the secondary use of data. Reporting requirements for this non-interventional study are described in Module VI Good Pharmacovigilance Practices, VI.C.1.2.1. Non-interventional Studies. "Real-time" adverse reaction reporting is not required, as described in Good Pharmacovigilance Practices (Module VI) and in the relevant section within Module VIII on the PASS:

• "for non-interventional study designs which are based on secondary use of data, adverse reactions reporting is not required. Reports of adverse events/reactions should only be summarised in the study report, where applicable"

However, as described in the modules for both the Periodic Safety Update Report (PSUR) (Module VII) and the Risk Management Plan (RMP) (Module V), information on collected adverse events will be included in the study report and reported appropriately in both the PSUR and the RMP. In cases of doubt, the reporting requirement will be clarified with the concerned authorities in EU Member States. Information on adverse events other than MDS disease progression, progression to AML, and SPM other than AML, (which is considered as disease progression in patients with MDS), will be collected using the Common Terminology Criteria for Adverse Events (CTCAE) to identify the incidence, but not the severity, of retrospectively identified adverse events. The CTCAE will be used where feasible to provide a common definitional framework for the adverse events collected as part of this study.

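### The Abstract promises adverse-event severity that the rest of the protocol does not collect, and acute adverse events are gathered over all follow-up with no stated risk window or denominator

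*Protocol*

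**What the plan says.** **Severity.** The safety paragraph of the Abstract (Data Analysis) says that safety in both cohorts will be "determined based on the incidence and severity (using AE definitions from NCI CTCAE where feasible". Section 9 says that CTCAE will be used "to identify the incidence, but not the severity, of retrospectively identified adverse events". Section 7.7.3, the methods text that the Abstract summarises, reads: "Safety for the on- and off-label cohorts will be determined based on the incidence of reported hematological and non-hematological adverse events". Table 5 in Section 7.3 defines the AE variable as "Date of event (incidence) (using case definitions from NCI CTCAE where feasible" and has no grade field.

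**Observation window.** Section 7.1.1 collects data from the first lenalidomide dose "until the date of death or last follow-up available at the time of the retrospective data collection (whichever occurs first", and adds "including for patients lost to follow-up or who discontinue the drug for any reason". Section 7.7.3 names neutropenia, thrombocytopenia, venous thromboembolism, infection, bleeding, major cardiac events and second primary malignancies (SPM), and says that they "will be collected throughout the observational period of a patient in both cohorts as part of the clinical routine". The protocol gives no end-of-treatment or AML cut-off for AEs.

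**Related statements.** Time to any event is counted from first dose (Section 7.1.1). Duration of exposure and dose interruptions are to be summarised (Abstract, Study drug exposure). Table 4 lists indication, starting dose, adjustments and interruptions, but no explicit stop date. Safety analyses are mainly descriptive or exploratory (Section 7.7.3), and no formal safety comparison of the cohorts is planned (Abstract, Sample Size Estimation).

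**The concern.** Describing safety inside and outside the EU indication is the secondary objective, and Section 7.9 says that the study should show the consequences of off-label prescribing for the safety profile. Two things stand in the way.

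First, a reader of the Abstract will expect severity results. Nothing in the methods or the variable tables would produce them, and Section 9 rules them out.

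Second, an infection or cytopenia that occurs well after the last dose, under a later therapy or after AML, falls inside the same collection window as one in the first cycle. If the report gives only the proportion of patients with an event, the cohort followed longer will tend to show more events even when the underlying rate is the same. The results will stand side by side in the report whether or not a formal test is done.

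**Working it through.** **1. Severity: the places side by side.**

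| Place | Incidence | Severity |
|---|---|---|
| Abstract, Safety analysis | yes | yes |
| Abstract, Variables (AEs) | yes | not mentioned |
| Section 7.3, Table 5 | event date | no grade field |
| Section 7.7.3 | yes | not mentioned |
| Section 9 | yes | explicitly excluded |

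One place promises severity, three do not provide for it and one excludes it. No SAP can satisfy both the Abstract's safety paragraph and Section 9.

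**2. Window: what is fixed and what is open.** Fixed: collection runs from first dose to death or last follow-up, including time after discontinuation. By contrast, Tables 3 and 4 stop some other items (blast count, transfusions) at disease progression. Open: whether incidence means a proportion or a rate, and which part of the window counts for acute AEs.

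**3. How much could it matter?** The protocol gives no AE figure to reproduce, no AE rate and no follow-up distribution. The inputs below are therefore assumptions. With a constant rate r per year, the same in both cohorts, and follow-up of t years, the crude proportion is 1 − exp(−r·t).

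| r per year | Follow-up (years) | Crude proportions | Ratio |
|---|---|---|---|
| 0.1 | 3 vs 2 | 25.9% vs 18.1% | 1.43 |
| 0.1 | 4 vs 2 | 33.0% vs 18.1% | 1.82 |
| 0.1 | 5 vs 1.5 | 39.3% vs 13.9% | 2.82 |
| 0.1 | 4 vs 1 | 33.0% vs 9.5% | 3.46 |
| 0.2 | 3 vs 2 | 45.1% vs 33.0% | 1.37 |
| 0.2 | 4 vs 2 | 55.1% vs 33.0% | 1.67 |
| 0.2 | 5 vs 1.5 | 63.2% vs 25.9% | 2.44 |
| 0.2 | 4 vs 1 | 55.1% vs 18.1% | 3.04 |

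The true rate ratio is 1 in every row. With equal follow-up the crude ratio is also 1.

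**4. Events after stopping.** Assume 0.3 events per year on drug and 0.1 off drug, with d years of treatment within f years of follow-up. The share of expected events after stopping is 0.1(f − d) / [0.3d + 0.1(f − d)].

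- d = 1, f = 2: 0.1/0.4 = 25%
- d = 2, f = 4: 0.2/0.8 = 25%
- d = 1, f = 4: 0.3/0.6 = 50%
- d = 0.5, f = 4: 0.35/0.5 = 70%

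**5. Why person-years alone do not settle it.** In the same model with d = 1, the full-follow-up rate is 0.4/2 = 0.20 per year when f = 2 and 0.6/4 = 0.15 when f = 4, although the on-drug rate is 0.3 in both. A front-loaded pattern is plausible here. Section 5.2 reports that the most frequent grade 3 and 4 events in the Phase 3 study were more common in Cycles 1 and 2. Hence the case for an on-treatment table beside the rates.

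**The case against.** The strongest reply is that collection is not analysis. Collecting to last follow-up is needed for SPM, which stands in the same sentence as the acute events. No text says that late acute events will be tabulated as on-drug events, or that a crude proportion is the only measure. Section 7.7 calls itself an overview and leaves detail to the SAP and to framework documents for the data owners. Event dates and first-dose dates are planned variables, and duration of exposure is to be summarised, so rates or an on-treatment table remain possible where registries hold the data. No formal safety comparison is planned.

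Most of this stands. A reader might infer that the protocol has chosen to analyse AEs without person-time, or that AE results cannot be attributed or compared at all. The documents support neither. The denominator is unstated, which the SAP may remedy, and the safety results are descriptive. Nor can it be said that follow-up does differ between the cohorts. Section 5.2 gives reason to expect earlier AML with additional cytogenetic abnormalities. However, the off-label cohort also takes patients who miss the label only on transfusion burden, and US registry patients whatever their start date, so even the direction is uncertain.

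The reply does not reach the severity contradiction, which lies wholly within the protocol. It also leaves a practical point. Raw data cannot be pooled (Section 7.9) and most analyses use aggregated data (Section 7.4), so window and denominator need to be settled before registries deliver their results.

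**Conclusion.** The severity contradiction is certain and needs no assumption: the Abstract's safety paragraph disagrees with Section 9 and has no support in Section 7.7.3 or Table 5.

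The window point holds as a conditional. Acute AEs are collected over all follow-up, including after discontinuation, so a crude proportion per cohort would be hard to interpret if follow-up or treatment duration differs. The size cannot be derived from the protocol. It is nil with equal follow-up and runs from 1.37 to 3.46 in the assumed cases above, which rest on constant and equal event rates. Full follow-up remains right for AML, SPM and death. This is a worthwhile, inexpensive improvement to a descriptive analysis and does not invalidate the safety objective.

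**What to change.** 1. **Severity.** Either delete the reference to severity from the Abstract's safety paragraph, or add CTCAE grade to Table 5 where a registry records it and bring Sections 7.7.3 and 9 into line. The first is a change of wording only. The second depends on what the registries hold.

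2. **Rates for acute AEs** (not AML, SPM or death). State in Section 7.7.3 that these are reported as events per 100 person-years with 95% CI, by cohort, over full follow-up. This uses first-dose date, event date and last follow-up, all already planned. Each registry can return event counts and summed person-years without releasing individual data.

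3. **On-treatment tabulation.** Add a table from first to last dose plus a lag fixed in advance, censored at AML, for registries that hold treatment stop dates. List the stop date explicitly in Table 4.

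The cost is small: protocol wording, one added variable and two further columns in the data request. The downside is that registries without stop dates contribute only to the full-follow-up rates. The on-treatment table should therefore accompany those rates, not replace them, and should state which registries it covers.
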